8.1.2. Body Investigator Global Assessment (B-IGA)

The scale, grade, and description for the B-IGA, is identical to the S-IGA, as discussed in Section 8.1. This endpoint will be analyzed in the same manner as S-IGA (Section 8.1.1).

8.1.3. Hypothesis Testing

Primary hypothesis testing will be performed independently on the two co-primary endpoints. The null hypothesis is that S-IGA/B-IGA Success at Week 8 does not differ between roflumilast foam 0.3% and matching vehicle foam. The alternative hypothesis is that the S-IGA/B-IGA Success at Week 8 does differ between roflumilast foam 0.3% and matching vehicle foam.

Null Hypothesis (H_0): $P_R Q_V / P_V Q_R = 1.0$,

Alternative Hypothesis (H_A): $P_R Q_V / P_V Q_R \neq 1.0$, where

P_R = the proportion of S-IGA/B-IGA Success in roflumilast foam 0.3%

P_V = the proportion of S-IGA/B-IGA Success in matching vehicle foam

$Q_R = 1 - P_R$

$Q_V = 1 - P_V$.

Each co-primary endpoint will be tested with using 2-sided alpha value of 0.025. The null hypotheses of no difference in S-IGA/B-IGA Success at Week 8 between roflumilast foam 0.3% and matching vehicle foam will be rejected if the two individual tests are significant.

8.1.4. Sensitivity and Supplemental Analyses

The following sensitivity and supplemental analyses will be performed for S-IGA and B-IGA, based on the CMH test as described in [Sections 8.1.1 and 8.1.2](#). Analyses of observed data will utilize the same CMH method but will not require the combination of multiple estimates required for the analyses with multiple imputation.:

- The two co-primary efficacy endpoints analyses repeated on subjects in the PP population using observed data.
- The two co-primary efficacy endpoint analyses repeated on subjects in the mITT population using MI data.
- The two co-primary efficacy endpoints analyses repeated on subjects in the ITT population using observed data.
- The two co-primary efficacy endpoints analyses repeated on subjects in the ITT population using a non-responder imputation in which the post baseline missing will be imputed as non-responder, meaning no S-IGA or B-IGA success.
- The tipping point analysis as described in [Section 6.1.4.2](#)
- The co-primary efficacy endpoints analyses repeated on subjects in the ITT population using MI imputed data, using the CMH model but excluding site as a stratification factor.

8.1.5. Impact of Site

The following supportive analysis will be performed to investigate the impact of site on the co-primary endpoints.

- To access the impact of pooled site on the primary analysis endpoint, the proportion of subjects achieving S-IGA success within each site will be plotted by treatment groups.
- An additional analysis to examine the impact of pooled study site will examine the changes in p-values that occur after removal of a pooled site from the overall analysis. First, remove one pooled site from the MI datasets, recalculate the combined CMH p-value as described for the primary analysis, and repeat removing a different site for each iteration. The p-values from the iterations will be plotted by the pooled site removed.

8.2. Secondary Efficacy Analyses

All secondary efficacy analyses will be performed using the ITT population, unless otherwise specified, on both observed and multiple imputation data. The non-responder imputation analysis will also be performed for secondary endpoints.

8.2.1. Scalp Itch – Numeric Rating Scale (SI-NRS)

The SI-NRS scale ranges from 0 to 10 with 0 being “no scalp itch” and 10 equaling “worst scalp itch imaginable.” This will be determined by asking the subject’s assessment of worst scalp itch over the past 24 hours.

Secondary efficacy endpoints relating to SI-NRS are all based on average weekly SI-NRS unless specified otherwise. The SPRU4-ITT population will be used for analyses of SI-NRS success. For other SI-NRS related endpoints, the ITT population will be used.

- For the subjects with baseline SI-NRS ≥ 4 , achievement of SI-NRS Success at Week 8
- For the subjects with baseline SI-NRS ≥ 4 , achievement of SI-NRS Success at Week 4
- For the subjects with baseline SI-NRS ≥ 4 , achievement of SI-NRS Success at Week 2
- SI-NRS CFB at Week 1
- SI-NRS CFB at 72 hours (daily score)
- SI-NRS CFB at Day 1(daily score)

SI-NRS Success Analysis

The estimand attributes (Section 8.1) can be described similarly to those described for the co-primary endpoints with the exception that the population of interest is changed to subjects with a baseline SI-NRS score ≥ 4 . This endpoint will be analyzed in the same manner as S-IGA (Section 8.1.1).

Change in SI-NRS Score Analysis

Change from baseline is the primary population level summary for this estimand, and all other attributes are identical to those specified for the co-primary endpoints. Percent change from

baseline is included as a supplemental summary measure. As specified in Section 2.2.2.2, timepoints of primary interest include Day 1 in daily SI-NRS score, 72 hours in daily SI-NRS score, and Week 1 in average weekly SI-NRS score. The analysis will include descriptive summaries of observed data as well as analyses based on multiple imputation datasets using the ITT population. ANCOVA with terms for pooled site group, baseline S-IGA category, baseline B-IGA category, and baseline SI-NRS score as covariates. The LS means, SEs, 95% CIs, 97.5% CIs, and *P* values will be presented. Refer to Section 6.1.4 for additional details.

Plots of daily SI-NRS (mean and SE of observed value and percent change from baseline) will be provided by treatment groups.

Other efficacy endpoints relating to daily SI-NRS

- Analysis of change and percent from baseline of SI-NRS daily scalp itch assessment will be performed using descriptive summaries. This will be summarized by study day.
- Similar ANCOVA model will be performed for change and percent change from baseline daily SI-NRS every day in the first week, at week 2, 4 and 8

8.2.2. Worst Itch – Numeric Rating Scale (WI-NRS) Pruritus Score

The WI-NRS scale ranges from 0 to 10 with 0 being “no scalp itch” and 10 equaling “worst imaginable itch.” This will be determined by asking the subject’s assessment of worst scalp itch over the past 24 hours.

The secondary efficacy endpoint relating to WI-NRS pruritus score, which is based on average weekly WI-NRS unless specified otherwise, is:

- For the subjects with baseline WI-NRS score ≥ 4 , achievement of at least 4-point improvement from baseline in WI-NRS at Week 8 (“WI-NRS Success at Week 8”)

WI-NRS Success Analysis

The estimand attributes (Section 8.1) can be described similarly to those described for the co-primary endpoints with the exception that the population of interest is the PRU4-ITT population. This endpoint will be analyzed in the same manner as S-IGA (Section 8.1.1).

8.2.3. Psoriasis Area and Severity Index (PASI)

Psoriasis Area and Severity Index (PASI) is used for the measurement of severity of psoriasis.

PASI combines the assessment of the severity of lesions and the area affected into a single score in the range 0 (no disease) to 72 (maximal disease).

The secondary efficacy endpoints relating to PASI score are:

- PASI-75 at Week 8
- CFB in PASI at Week 2

PASI-75 Analysis

The estimand attributes (Section 8.1) can be described similarly to those described for the co-primary endpoints. This endpoint will be analyzed in the same manner as S-IGA (Section 8.1.1).

Change in PASI Score Analysis

Change in the PASI total score from baseline to Week 2 will be analyzed in the same way as change from baseline in SI-NRS (Section 8.2.1).

8.2.4. Psoriasis Symptoms Diary (PSD)

The PSD assesses the severity of symptoms or how bothersome are the symptoms of psoriasis. The total score combines the scores of the 16 individual questions into a single score in the range of 0 to 72 (individual questions scored 0 to 10, where higher scores indicate more severe symptoms).

The secondary efficacy endpoints relating to PSD score are:

- CFB in PSD Items related to Itching, Pain, and Scaling (Questions 1, 9, and 11) aggregate score at Week 8
- PSD Item related to Scaling (Question 11) = 0 at Week 8
- PSD Item related to Itching (Question 1) = 0 at Week 8
- PSD Item related to Pain (Question 9) = 0 at Week 8
- PSD Total Score = 0 at Week 8

Change in Total PSD Score Analysis

Change in the PSD score from baseline to Week 2, 4, and 8 will be analyzed in the same way as change from baseline in SI-NRS (Section 8.2.1).

The occurrence of PSD itching, scaling, pain, and total scores of 0 will be analyzed with methods previously described for the primary efficacy endpoints (Section 8.1.1).

8.2.5. Psoriasis Scalp Severity Index (PSSI)

The PSSI is used to measure the severity of psoriasis, combining the assessment of the severity of scalp lesions and the area of scalp affected into a single score ranging from 0 (no disease) to 72 (maximal disease).

The secondary efficacy endpoint relating to PSSI score is:

- PSSI-75 at Week 8

PSSI-75 Analysis

The estimand attributes (Section 8.1) can be described similarly to those described for the co-primary endpoints. This endpoint will be analyzed in the same manner as S-IGA (Section 8.1.1).

8.2.6. Scalp Investigator Global Assessment (S-IGA)

The secondary efficacy endpoints relating to S-IGA score are:

- S-IGA score of “Clear” at Week 8
- S-IGA Success at Week 4
- S-IGA Success at Week 2

S-IGA Categorical Analysis

The estimand attributes (Section 8.1) can be described similarly to those described for the co-primary endpoints. This endpoint will be analyzed in the same manner as S-IGA (Section 8.1.1).

A summary of primary and secondary efficacy analyses is shown in Table 5.

Table 5: Summary of Primary and Secondary Efficacy Analyses

| Efficacy Endpoint | Primary Analysis | Sensitivity or Supplemental Analysis |
|--|--------------------------------|---|
| Primary ($\alpha = 0.025$) | | |
| S-IGA Success (IGA score of ‘0’ or ‘1’ plus at least 2-point improvement from baseline) at week 8 | ITT, multiple imputation (CMH) | #1 PP, observed data (CMH) #2 mITT, multiple imputation (CMH) #3 ITT, observed data (CMH) #4 ITT, non-responder imputation (CMH) #5 ITT, Tipping point #6 ITT based on different site pooling strategy #7 ITT without site stratification |
| B-IGA Success (IGA score of ‘0’ or ‘1’ plus at least 2-point improvement from baseline) at week 8 | ITT, multiple imputation (CMH) | #1 PP, observed data (CMH) #2 mITT, multiple imputation (CMH) #3 ITT, observed data (CMH) #4 ITT, non-responder imputation (CMH) #5 ITT, Tipping point #6 ITT based on different site pooling strategy #7 ITT without site stratification |
| Secondary Family 2 ($\alpha=0.005$) | | |

| | | |
|---|---|---|
| Family 1 ($\alpha=0.01$ or 0.015): Average weekly SI-NRS Success (achievement of at least a 4-point improvement) at Weeks 2, 4, 8 | SPRU4-ITT population, multiple imputation (CMH, odds ratio) | #1 SPRU4-ITT, observed data (CMH) #2 SPRU4-ITT, non-responder imputation (CMH) |
| Family 1 ($\alpha=0.01$ or 0.015): 
 • SI-NRS change from baseline at Week 1 • SI-NRS change from baseline at 72 hours • | ITT population, multiple imputation, ANCOVA | #1 ITT, observed data |
| Family 2 ($\alpha=0.005$): Average weekly WI-NRS Success (achievement of at least a 4-point improvement) at Week 8 | PRU4-ITT, multiple imputation (CMH) , odds ratio) | #1 ITT, observed data (CMH) #2 ITT, non-responder imputation (CMH) |
| Family 2 ($\alpha=0.005$): PASI-75 at Week 8 | ITT, multiple imputation (CMH) | #1 ITT, observed data (CMH) #2 ITT, non-responder imputation (CMH) |
| Family 2 ($\alpha=0.005$): CFB in PSD Items related to Itching, Pain, and Scaling (Questions 1, 9, and 11) aggregate score at Week 8 | ITT, multiple imputation, ANCOVA | #1 ITT, observed data |
| Family 2 ($\alpha=0.005$): 
 • PSD Item related to Scaling (Question 11) = 0 at Week 8 • PSD Item related to Itching (Question 1) = 0 | ITT, multiple imputation (CMH) | #1 ITT, observed data (CMH) #2 ITT, non-responder imputation (CMH) |

| | | |
|--|---|---|
| at Week 8 
 PSD Item related to Pain (Question 9) = 0 at Week 8 | | |
| Family 2 ($\alpha=0.005$): PSSI-75 at week 8 | ITT, multiple imputation (CMH) | #1 ITT, observed data (CMH) #2 ITT, non-responder imputation (CMH) |
| Family 3 ($\alpha=0.01$ or 0.02 or 0.025): S-IGA score of 'Clear' at Week 8 | ITT, multiple imputation (CMH) | #1 ITT, observed data (CMH) #2 ITT, non-responder imputation (CMH) |
| Family 3 ($\alpha=0.01$ or 0.02 or 0.025): S-IGA success at week 4, 2 | ITT, multiple imputation (CMH) | #1 ITT, observed data (CMH) #2 ITT, non-responder imputation (CMH) |
| Family 3 ($\alpha=0.01$ or 0.02 or 0.025): Change from baseline in PASI at week 2 | ITT, multiple imputation, ANCOVA | #1 ITT, observed data |
| Family 3 ($\alpha=0.01$ or 0.02 or 0.025): PSD Total Score = 0 at Week 8 | ITT, multiple imputation (CMH) | #1 ITT, observed data (CMH) #2 ITT, non-responder imputation (CMH) |
| Family 3 ($\alpha=0.01$ or 0.02 or 0.025): SI-NRS change from baseline at Day 1 | ITT population, multiple imputation, ANCOVA | #1 ITT, observed data |

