5.2.8. Psoriasis Symptom Diary (PSD)

The PSD will be performed at study visits according to the Schedule of Visits and Assessments ([Section 1.3](#)). The PSD includes items related to Itching (question 1), Pain (question 9) and Scaling (question 11).

Only adult subjects will complete the PSD. See [Appendix 6](#) for the PSD.

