3.3. Study Population

Study population consists of male and female adolescents (12-17 years old) and adults (≥ 18 years old). Subjects should have a minimum S-IGA of at least “Moderate” (3) and B-IGA

of at least “Mild” (2) at baseline.

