- d. Height will be collected at Screening and Week 8. Weight will be collected at all study visits. Subjects should void prior to weight being taken and remove any objects of significant weight (i.e., jackets, outerwear, shoes, cell phones, wallet, key chains, etc.). A 5% unintentional weight loss from Baseline should be reported to the medical monitor.
- e. S-IGA will be a 5-point scale ranging from clear (0) to severe (4) and is evaluated for the scalp only. B-IGA will use the same scale as S-IGA but will evaluate the entire body (except the scalp, palms, and soles). PSSI is scored on a 0-72 scale and evaluates the scalp only. PASI assessment should exclude palms and soles. **S-IGA and B-IGA should be completed prior to other Investigator assessments and every effort should be made for the same evaluator to complete at each study visit.**
- f. Total BSA affected by scalp and body psoriasis will be determined by the subject's hand method, where the subject's hand (including fingers) surface area is assumed to equal 1% of body surface area. Scalp will be included in total BSA measurement, but palms and soles will be excluded. The total scalp (ie, 100% of the total scalp surface area) can be considered to be approximately 4% BSA.
- g. Extent of scalp involvement will be the extent of psoriasis involved, expressed as a percentage of total scalp.
- h. The DLQI will be completed by subjects ≥ 17 years of age. The CDLQI will be completed for subjects 12 to 16 years old, inclusive. Scalpdex will be completed by all subjects. PSD will be completed by subjects ≥ 18 years of age.
- i. Subjects/parents/caregivers will complete the SI-NRS and WI-NRS daily at home starting 7 days prior to the Baseline/Day 1 visit to Day 57 (Week 8) visit. Daily SI-NRS and WI-NRS will be completed in the evening prior to IP application (except at Baseline and Week 2 when IP is applied at the clinic). **The SI-NRS should be completed first and then WI-NRS.**
- j. Local tolerability assessments include both investigator and subject assessments. The Investigator assessment of skin irritation (Berger and Bowman skin irritation score) is to be recorded prior to IP application.

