5. ANALYSIS POPULATIONS

The following analysis populations are planned for this study:

- **Safety Population (SAF):** The Safety population will include all subjects who are randomized and received at least 1 confirmed dose of investigational product (IP). This population will be used for all safety analyses.
- **Intent-To-Treat Population (ITT):** The ITT population will include all randomized subjects. This population will be the primary analysis population for the analysis of efficacy endpoints, along with subject disposition.

- **Per Protocol (PP) Population:** The PP population will include the subjects in the ITT population who were at least 80% compliant with study drug application, have an S-IGA and B-IGA assessment at Week 8, and showed no important deviations from the study protocol that would affect the interpretation of efficacy. “Important deviations” will result from a blinded review at the end of the study and the team will determine the important deviations that can impact on efficacy. This population will be used for a supplemental analysis for primary efficacy endpoints.
- **Modified Intent-to-Treat Population (mITT):** The mITT population includes all randomized subjects with the exception of subjects who missed the Week 8 S-IGA or B-IGA assessment specifically due to COVID-19 disruption. This population will be used for sensitivity of the primary endpoints.
- **Scalp Pruritus ITT Population (SPRU4-ITT):** The SPRU4-ITT population is a subset of the ITT population and includes subjects with average weekly SI-NRS score ≥ 4 at baseline. This population will be used for the analysis of achievement of at least 4-point reduction in average weekly SI-NRS score as compared to baseline.
- **Pruritus ITT Population (PRU4-ITT):** The PRU4-ITT population is a subset of the ITT population and includes subjects with average weekly WI-NRS score ≥ 4 at baseline. This population will be used for the analysis of achievement of at least 4-point reduction in average weekly WI-NRS score as compared to baseline.
- **Pharmacokinetic Population (PK):** The PK population will include all subjects who received at least one confirmed dose of investigational product (IP) and provided at least one PK sample. This population will be used for summary of PK concentration results for subjects who applied roflumilast foam 0.3% during this study.

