14.1. Planned Table Descriptions

The following are planned summary tables for protocol number ARQ-154-309. The table numbers are place holders only and may be changed when the tables are produced.

| Table Number | Population | Table Title/Summary |
|------------------|-----------------------------|--|
| 14.1 | | Disposition, Baseline Characteristics and Exposure Summary |
| 14.1.1 | All Subjects | Subject Disposition |
| 14.1.2.1 | ITT | Demographics and Baseline Characteristics |
| 14.1.2.1 (cont.) | ITT | Demographics and Baseline Characteristics |
| | | |
| 14.1.2.1 (cont.) | ITT | Demographics and Baseline Characteristics |
| 14.1.2.1 (cont.) | ITT | Demographics and Baseline Characteristics |
| 14.1.2.1 (cont.) | ITT | Demographics and Baseline Characteristics |
| 14.1.2.1 (cont.) | ITT | Demographics and Baseline Characteristics |
| 14.1.2.2 | Safety | Demographics and Baseline Characteristics |
| 14.1.3 | Safety | Previous Treatment History of Scalp and Body Psoriasis |
| 14.1.4 | ITT | Protocol Deviations |
| 14.1.5 | Safety | Prior Medications by Anatomic Therapeutic Chemical (ATC) Class Level 4 and Preferred Term |
| 14.1.6 | Safety | Summary of Study Drug Exposure |
| 14.2 | | Efficacy Summary |
| 14.2.1 | ITT, SPRU4-ITT, or PRU4-ITT | Hypothesis Testing for Primary and Secondary Efficacy Endpoints - Multiple Imputation |
| 14.2.1.1 | ITT | Scalp Investigator Global Assessment (S-IGA) Grades and Success by Study Visit – Multiple Imputation (Primary Analysis) Categorical Results |
| 14.2.1.1.s | ITT | Scalp Investigator Global Assessment (S-IGA) Grades and Success by Study Visit – Multiple Imputation (Primary Analysis, Supplemental Estimand) Categorical Results |
| 14.2.1.2 | mITT | Scalp Investigator Global Assessment (S-IGA) Grades and Success by Study Visit – Multiple Imputation (Sensitivity Analysis) Categorical Results |
| 14.2.1.3 | ITT | Scalp Investigator Global Assessment (S-IGA) Grades and Success by Study Visit – Observed Data (Sensitivity Analysis) Categorical Results |
| 14.2.1.4 | Per-protocol | Scalp Investigator Global Assessment (S-IGA) Grades and Success by Study Visit – Observed Data (Supplemental Analysis) Categorical Results |
| 14.2.1.5 | ITT | Scalp Investigator Global Assessment (S-IGA) Grades and Success by Study Visit – Non-responder Imputation (Sensitivity Analysis) Categorical Results |

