| 14.2.6.6 | ITT | Summary of Psoriasis Scalp Severity Index (PSSI) by Study Visit – Observed Data (ANCOVA) |
| 14.2.6.7 | ITT | Summary, Change and Percent Change from Baseline in Psoriasis Scalp Severity Index (PSSI) by Study Visit – Observed Data |
| 14.2.7.1.1 | ITT - Patients with Age ≥ 18 years | Summary of Psoriasis Symptoms Diary (PSD) Aggregate Score of Itching/Pain/Scaling by Study Visit – Multiple Imputation (ANCOVA) |
| 14.2.7.1.1.s | ITT - Patients with Age ≥ 18 years | Summary of Psoriasis Symptoms Diary (PSD) Aggregate Score of Itching/Pain/Scaling by Study Visit – Multiple Imputation (ANCOVA) (Secondary Analysis, Supplemental Estimand) |
| 14.2.7.1.2 | ITT - Patients with Age ≥ 18 years | Summary, Change, and Percent Change from Baseline in Psoriasis Symptoms Diary (PSD) Aggregate Score of Itching/Pain/Scaling by Study Visit – Multiple Imputation |
| 14.2.7.1.3 | ITT - Patients with Age ≥ 18 years | Summary of Psoriasis Symptoms Diary (PSD) Aggregate Score of Itching/Pain/Scaling by Study Visit – Observed Data (ANCOVA) |
| 14.2.7.1.4 | ITT - Patients with Age ≥ 18 years | Summary, Change, and Percent Change from Baseline in Psoriasis Symptoms Diary (PSD) Aggregate Score of Itching/Pain/Scaling by Study Visit – Observed Data |
| 14.2.7.2.1 | ITT - Patients with Age ≥ 18 years | Achievement of Score of 0 for Psoriasis Symptoms Diary (PSD) Item Related to Scaling by Study Visit – Multiple Imputation |
| 14.2.7.2.1.s | ITT - Patients with Age ≥ 18 years | Achievement of Score of 0 for Psoriasis Symptoms Diary (PSD) Item Related to Scaling by Study Visit – Multiple Imputation (Secondary Analysis, Supplemental Estimand) |
| 14.2.7.2.2 | ITT - Patients with Age ≥ 18 years | Achievement of Score of 0 for Psoriasis Symptoms Diary (PSD) Item Related to Scaling by Study Visit – Observed Data (Sensitivity Analysis) |

| | | |
|--------------|---|--|
| 14.2.7.2.3 | ITT - Patients with Age ≥ 18 years | Achievement of Score of 0 for Psoriasis Symptoms Diary (PSD) Item Related to Scaling by Study Visit – Non-responder Imputation (Sensitivity Analysis) |
| 14.2.7.3.1 | ITT - Patients with Age ≥ 18 years | Achievement of Score of 0 for Psoriasis Symptoms Diary (PSD) Item Related to Itching by Study Visit – Multiple Imputation |
| 14.2.7.3.1.s | ITT - Patients with Age ≥ 18 years | Achievement of Score of 0 for Psoriasis Symptoms Diary (PSD) Item Related to Itching by Study Visit – Multiple Imputation (Secondary Analysis, Supplemental Estimand) |

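### The SAP gives two different analysis populations for the five alpha-controlled PSD endpoints: all randomized subjects in Table 5 and Table 14.2.1, adults only in Tables 14.2.7.x

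*SAP*

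**What the plan says.** On who is assessed, the documents agree. Protocol 5.2.8: "Only adult subjects will complete the PSD". SAP Table 1, footnote h: "PSD will be completed by subjects" aged 18 or over. The trial also enrolls younger subjects; SAP 3.3: "Study population consists of male and female adolescents (12-17 years old) and adults". An adolescent therefore has no PSD value at any visit, Baseline included.

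On who is analyzed, the SAP says two things.

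- **All randomized subjects.** SAP 5: "The ITT population will include all randomized subjects". SAP 8.2: "All secondary efficacy analyses will be performed using the ITT population, unless otherwise specified, on both observed and multiple imputation data". Table 5 (under 8.2.6) gives the aggregate itching, pain and scaling endpoint as "aggregate score at Week 8 | ITT, multiple imputation, ANCOVA". It lists the four zero-score endpoints (scaling, itching, pain, total) as ITT with multiple imputation and CMH, and their observed-data and non-responder sensitivity analyses also as ITT. Sections 8.2.4 and 6.1.4.1.1 give no age limit. Table 14.2.1, which collects the hypothesis tests, has the population "ITT, SPRU4-ITT, or PRU4-ITT".
- **Adults only.** In SAP 14.1 the Population column of every PSD table, 14.2.7.1.1 to 14.2.7.7.2, reads "ITT - Patients with Age ≥ 18 years". This covers multiple imputation, observed data, non-responder imputation and the supplemental estimand.

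**The concern.** A questionnaire that is not given to a subject by design does not produce missing data, so imputing it, or scoring its absence as failure, has no clear meaning. The SAP shows how to handle a restricted endpoint: for the itch-success endpoints it defines SPRU4-ITT and PRU4-ITT in Section 5 and uses them for the main analyses in Table 5. It did not do the same for the PSD, so a programmer working from Table 5 and one working from Tables 14.2.7.x would use different denominators.

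The position of these endpoints raises the stakes. Four are steps 3 to 6 of the seven in Family 2, tested in sequence at 0.005. A failure at any of them ends Family 2 before PSSI-75, leaves Family 1 at 0.01 instead of 0.015, and rules out the full 0.025 for Family 3. The fifth, a PSD total score of zero, is in Family 3. SAP Version 3.0 was written after database lock and unblinding, when a gatekeeping test should leave no choice of denominator.

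**Working it through.** **1. Count.** Families 1, 2 and 3 hold 5 + 7 + 6 = 18 endpoints. PSD endpoints: 4 in Family 2 and 1 in Family 3, so 5 of 18.

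**2. What the Table 5 reading does to an adolescent.** Step 2 of SAP 6.1.4.1.1 predicts each visit from earlier outcomes, pooled site and treatment, and its code includes the baseline score among the variables to be imputed. An adolescent has no earlier PSD outcome, so baseline is generated from treatment and site alone, and every later visit from those plus generated values. The ANCOVA for the aggregate score would then use a generated baseline as covariate. SAP 6.1.7 sets continuous outcomes to baseline after discontinuation for adverse event or lack of efficacy; an adolescent has no observed PSD baseline to be set to. Under non-responder imputation the adolescent is a failure. Under Tables 14.2.7.x the same subject is left out and none of this arises.

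**3. Size under failure scoring.** The documents give no PSD rates, no PSD power and no adolescent share, so these are assumed. With share *f*, equal in both arms, both rates and their difference are multiplied by (1 − *f*). For an illustrative 25-point difference: *f* = 5% (420 × 0.05 = 21 subjects) gives 25 × 0.95 = 23.75; *f* = 10% (42 subjects) gives 25 × 0.90 = 22.5.

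Power uses the unstratified two-proportion approximation

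Φ[(d − z·SE0)/SE1], with SE0 = √(p̄(1 − p̄)(1/n1 + 1/n2)) and SE1 = √(p1(1 − p1)/n1 + p2(1 − p2)/n2).

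As a check on the method, 140 vs 280 subjects at two-sided 0.025 gives more than 99.99% for S-IGA (11% vs 46%) and 99.999% for B-IGA (7% vs 32%), in line with the SAP's figure of more than 99%.

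For the PSD, α = 0.005 two-sided, z = 2.807. Worked case, assumed 10% vehicle and 25% active, *f* = 15%:

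- Adults only: n = 119 and 238, d = 0.15, SE0 = 0.0449, SE1 = 0.0393; power 72.9%.
- Full ITT, adolescents as failures: n = 140 and 280, rates 8.5% and 21.25%, d = 0.1275, SE0 = 0.0389, SE1 = 0.0340; power 70.6%.

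| Assumed rates | *f* = 5% (21) | *f* = 10% (42) | *f* = 15% (63) |
|---|---|---|---|
| 10% vs 30% | 97.3 / 97.1 | 96.3 / 95.7 | 95.0 / 93.8 |
| 15% vs 35% | 93.8 / 93.3 | 92.2 / 90.9 | 90.1 / 87.8 |
| 5% vs 20% | 92.0 / 91.7 | 89.9 / 89.2 | 87.4 / 86.1 |
| 10% vs 25% | 79.6 / 78.9 | 76.4 / 74.9 | 72.9 / 70.6 |

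Each cell is power in percent, adults only / full ITT with adolescents as failures. The largest gap is about 2.3 points.

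**4. Size under multiple imputation.** This is the listed main analysis, and its effect was not quantified. The adolescents' values would be model output only, so they add subjects to the reported N without adding PSD information.

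**The case against.** The best reply is that the SAP already settles the matter. Section 8.2 makes ITT the default only where nothing else is specified, and Section 14.1 does specify something else, in the column meant for analysis populations. No dedicated PSD table on the full ITT set is planned. Table 5 is introduced as a summary and is loose elsewhere: it lists the WI-NRS success sensitivity analyses as ITT, while Tables 14.2.4.2 and 14.2.4.3 use PRU4-ITT. DLQI and CDLQI follow the same pattern, with ITT in Section 8.3 and age-limited sets in 14.1.

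Much of this stands. A reader might infer that adolescents' PSD values will in fact be invented or scored as failures. The documents do not support that: it follows only if Table 5 governs. A reader might also infer that the confirmatory table will carry different p-values from the detailed tables. That is not shown either; adults are a subset of ITT, and nothing says a separate full-ITT PSD test will be run for Table 14.2.1.

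What does not stand is that no correction is needed. Table 5 states a rule for these endpoints rather than leaving a gap, Table 14.2.1 does not list the adult subset, and neither the imputation section nor 8.2.4 limits the input. No sentence says that 14.1 takes precedence.

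**Conclusion.** This is an internal conflict over the analysis population of five alpha-controlled endpoints. Adults-only is the probable intention, and it is the only reading that fits an instrument given to adults. Read literally, Table 5 gives a wrong denominator and model-generated baselines at four consecutive gatekeeping steps. The numerical consequence is likely small: at most about 2.3 points of power in the failure-scoring scenario, across four assumed pairs of rates and adolescent shares up to 15%, with the share equal in both arms and stratification ignored. No inflation of type I error is shown. The case for acting rests on removing ambiguity from a gatekeeping sequence and on defining the endpoint only in subjects for whom it is measured.

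**What to change.** Apply the population already stated in Tables 14.2.7.x, ITT subjects aged 18 or over (those to whom the PSD is administered), in these places:

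- the PSD rows of Table 5, main and sensitivity analyses;
- the PSD entries of Table 6;
- Section 8.2.4;
- the Population cell of Table 14.2.1;
- Section 6.1.4.1.1, by limiting the PSD input data for imputation to that set.

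Because SAP Version 3.0 is a post-unblinding document, record the change as a clarification consistent with the existing 14.2.7.x populations, not as a new analysis set. The cost is a few lines of text; if any programming followed Table 5 literally, the affected PSD outputs would need to be rerun. The N for PSD endpoints falls by the number of adolescents randomized, relative to the Table 5 reading.
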